Category 2: Research involving greater than minimal risk, but presenting the prospect of direct benefit to the individual subjects.

E2. Subjects

Gender:

Both

Age:

Adult (18-64 yrs), Geriatric (65+ yrs)

Ethnicity:

All Ethnicities

Primary Language:

English, Spanish

Groups to be recruited will include:

Patients

Which if any of the following vulnerable populations will be recruited as subjects?

Vulnerable populations require special protections. How will you obtain informed consent, protect subject confidentiality, and prevent undue coercion?

E3. Pregnant woman/fetus

Will pregnant women and/or fetuses (as described in 45 CFR 46 Subpart B) be enrolled in the research?

No

E4. Neonates

Will neonates of uncertain viability or nonviable neonates (as described in 45 CFR 46 Subpart B) be enrolled in the research?

No

E5. Children

Will children be enrolled in the research?

No

Section F: Design/Procedure

F1. Design

Select one category that most adequately describes your research:

c) Pilot

Discuss the research design including but not limited to such issues as: probability of group assignment, potential for subject to be randomized to placebo group, use of control subjects, etc.

In this proof of concept, intent to treat trial, 15 consecutive patients with diabetes and risk for lower extremity ulcers will be recruited from all study sites. Patients will be consented per the local Institutional Review Board's guidelines and approval for this study.

Inclusion Criteria:

a) Males or females age 18-80 years old with history of type 1 or 2 diabetes and the ability and willingness to provide Informed consent b) Patients with diabetic foot ulcers c) Patient is willing to participate in all procedures and follow up evaluations necessary to complete the study. d) Patients who have undergone lower extremity surgery / amputation may be enrolled into the study to the clinical judgment of the Investigator

Exclusion Criteria:

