a) Patients with severe peripheral vascular disease (ABI or ankle brachial systolic pressure index <0.5) b) Patients with diabetic foot ulcers in the plantar surface of the medial longitudinal arch of the foot c) Patients with active wound infection, or untreated osteomyelitis d) Patients currently on immunosuppressive drugs. e) Pregnant or breastfeeding females. f) Acute fractures of the foot g) Acute heart failure h) Participation in an interventional Study within the last 30 days i) Non-ambulatory or unable to stand without help or walk a distance of at least 6 feet without assistance. k) Patients with major foot amputation. j) Patients who are unable or unwilling to participate in all procedures and follow up evaluations h) Patients who do not fit to available PulseFlow® sizes (UK 5-11, US 7-10.5) provided by the Diabetic Boot Company

F2. Procedure

Following is a summary of study procedures:

Study Day 0 (initiation), Visit 1 The following baseline values will be assessed and recorded. In needed assessments, the podiatric physician will examine the patient providing standard of care treatment.

Screening/ Baseline: Subjects will be screened to ensure that they meet the inclusion and exclusion criteria. The study will be explained and written informed consent obtained from each patient prior to the initiation of screening procedures.

Cognitive assessment: The Montreal Cognitive Assessment (MOCA) is a series of questions used to assess cognitive status.

Physical exam: Physical exam will be conducted, including vascular, dermatological, and neurological, as part of a regular care visit.

Medical History: A detailed medical history will include: previous medical history, location and duration of previous ulcers, amputation (toe, foot, below knee, above knee), lower extremity bypass, lower extremity angioplasty, CABG, cardiac angioplasty, last visit by physician (in weeks), and current/past use of special shoes or insoles.

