Assessment of user friendliness, acceptability, and perception of need: We will use a questionnaire tailored to the topic of this study to evaluate the perception of the target population in receiving benefit from the proposed technology. Subjects are asked to answer the questionnaire at the end of study. The questionnaire includes 11 items and allows assessing how target population perceives the need of such technology in management of their problem.

Other assessments: Other relevant assessments are Demographic/Health questionnaire, the Montreal Cognitive Assessment, the mobility-tiredness scale, Barthel Index, Depression Scale, fear of falling (Short-Falls Efficacy Scale – International), quality of life (Promise Global General Health Questionnaire), digital photography, Fried Frailty Criteria, Foot Questionnaire, Pain Assessment, Fall Log and Contact Agreement, Physical activity log, follow-up questionnaire, Shoe-fit test , subject’s perception assessment compared to standard shoe and RCW assessed using a 10 point Likert scale questionnaire.

PulseFlow DF: The PulseFlow device will be given to the subject. The research personnel will make sure that the subject is comfortable with the device and the device itself provides the offloading that is needed. The research personnel will also provide device education to the participants and will answer any questions that may arise.

Study Day 1, Visit 2 48-hour follow: All participants will be asked to return to clinic approximately 48 hours after visit 1. In this visit, (1) any adverse events will be assessed; (2) activity measurement (body sensor) will be returned; (3) PulseFlow DF data will be downloaded to ensure operability and patient compliance; and (4) further device education will be provided in case any issues have risen. We will take digital photographs of the participants feet and collect edema information.

Study Day 2, Visit 3 1-week follow-up: All participants will be asked to return to clinic approximately 1 week after visit 1. In this visit, (1) any adverse events will be assessed; and (2) PulseFlow DF data will be downloaded to ensure operability and patient compliance. Device education will be provided if needed. The participant will be asked to return the device at their next visit. We will take digital photographs of the participants feet and collect edema information.

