Study Day 3, Visit 4 4-week follow-up: All participants will be asked to return to clinic approximately 4 weeks after visit 1. In this visit, outcome assessment using similar assessments described for Study Day 0 will be performed. In addition, perception of benefit and user-friendliness of the PulseFlow DF® will be assessed using a questionnaire. We will take digital photographs.

Participants will be asked to wear a comfortable shirt which holds a small activity monitor (PAMSys) for a period of 48 Hours (2 days). Patients will be requested to return this device via a pre-paid FEDEX envelope

Study Day 4, Visit 5 Follow-up up to three months: Some participants may be contacted by the study coordinator approximately up to three months post the last study visit to document success of wound healing if they continue to use PulseFlow DF after 4 weeks as well as potential incident of re-ulceration, or incident of falls.

We will ask participants to provide an Emergency Contact.

We will ask participants if they would like to be contacted for further studies they may be eligible for.

****Please note that the protocol attached to Section S is from the University of Arizona. The PI initially established this protocol at U of A as it is an investigator initiated study. We have ensured that we have not included any references to U of A in this BCM protocol*****

Section G: Sample Size/Data Analysis

G1. Sample Size

How many subjects (or specimens, or charts) will be used in this study?

Local: 50 Worldwide: 50

Please indicate why you chose the sample size proposed:

We intend to employ a simple minimal risk research protocol to capture data required to realize the goals of this study. The results from this study will help us understand the real clinical needs and optimize the device specifications and form factor to fulfill these needs.

This is an initial proof of concept pilot study. The results of this study will allow for the calculation of an appropriate sample size for a larger proof of superiority (over current standard of care) trial.

G2. Data Analysis

Provide a description of your plan for data analysis. State the types of comparisons you plan (e.g. comparison of means, comparison of proportions, regressions, analysis of variance). Which is the PRIMARY comparison/analysis? How will the analyses proposed relate to the primary purposes of your study?

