The individual (PI, co-PI, study coordinator, or designee – interns) obtaining consent will be given a thorough training of the process and go through several mock consent scenarios. The training consists of understanding the study and being able to fully explain it to the participant providing all pertinent information (procedures, risks, benefits, alternatives to participant), giving sufficient time to the participant to consider whether or not they would like to participate, and answer any questions which the subject may have. The training will have a strong emphasis on subject comprehension of the research study by asking open-ended questions to the subject.

The patient will be informed that their participation is strictly voluntary and their choice will not affect future care with their care providers. We will also inform them that they are free to withdraw consent and discontinue participation in the project at any time, even after signing the informed consent document. At the end of the meeting, a signed informed consent form will be given to the patient for their records. Once the subject is providing his/her own consent for medical care and procedures, he/she will be asked for permission to continue to participate. The consent will be presented and discussed just as any initial consent process. The subject will then be given adequate time to read and discuss the study and make an informed decision about continuing to take part.

Patients will be referred by Co-PIs' practices including Wound Care Center at Southwest Memorial.

Please note that we will submit a Spanish consent for approval once the English one has been approved.

We also have attached the English questionnaires to Section S. We are not translating the questionnaires as we have Spanish speaking coordinators on staff to provide translation in these situations.

Are foreign language consent forms required for this protocol?

Yes

Which of the following ways will you document informed consent in languages other than English?

A full-length informed consent document

J3. Privacy and Intrusiveness

Will the research involve observation or intrusion in situations where the subjects would normally have an expectation of privacy?

No

J4. Children

Will children be enrolled in the research?

No

J5. Neonates

Will non-viable neonates or neonates of uncertain viability be involved in research?

No

J6. Consent Capacity - Adults who lack capacity

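### The Spanish wording and the translator of the repeated questionnaires are not fixed between baseline and 4 weeks, so a switch between visits enters the change in quality of life and fear of falling

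*Combined protocol and SAP*

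**What the plan says.** Section E2 gives the primary languages of the study population as "English, Spanish". Section J2 then deals with documents in other languages. For consent, a full-length Spanish form is planned: "Please note that we will submit a Spanish consent for approval once the English one has been approved". For the instruments the choice is different: "We also have attached the English questionnaires to Section S", followed by "We are not translating the questionnaires as we have Spanish speaking coordinators on staff to provide translation in these situations".

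Section F2, under the other assessments, lists a set of patient-reported scales that includes "fear of falling (Short-Falls Efficacy Scale – International), quality of life (Promise Global General Health Questionnaire". For the 4-week visit the same section says that "outcome assessment using similar assessments described for Study Day 0 will be performed", so scales given at baseline are to be given again.

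Section G2 makes quality of life part of H3, one of three hypotheses, and names SF12 as the variable. The covariates it gives as examples for that analysis are weather, BMI and age. It mentions neither language nor translator. Section D ranks quality of life and fear of falling among the other assessments, below the primary and secondary endpoints.

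**The concern.** A questionnaire score depends on the words the patient hears. With only English forms and more than one coordinator able to translate, a Spanish-speaking patient may hear one rendering of an item at baseline and another at 4 weeks, from the same coordinator or from two. The documents require no fixed Spanish text, no validated Spanish version and no continuity of translator.

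The study has no parallel control group, so the natural summary for these scales is the difference between the two visits. A rendering that stays constant would largely cancel in that difference. One that changes does not cancel and cannot be separated from a real change in the patient. What is at stake is the precision of the quality-of-life part of H3 and of the fear-of-falling result, together with any use of their variability in planning the larger trial that section G1 has in view.

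**Working it through.** **Step 1: which results are exposed.** Setting the sections side by side:

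- Ankle brachial index, skin perfusion pressure and plantar pressure (section D, primary) are instrument readings. Not exposed.
- Balance, activity and gait (section D, secondary) come from body-worn sensors. Not exposed.
- Quality of life (section D, other assessments; section G2, H3) is a questionnaire repeated at 4 weeks. Exposed.
- Fear of falling (section D, other assessments; section F2) is a questionnaire repeated at 4 weeks. Exposed. It is not a dependent variable in section G2.

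**Step 2: is there an offsetting safeguard?** None appears in sections F2, G2 or J2. The Spanish consent form shows that Spanish-speaking participants are expected, but the plan for a written Spanish text stops at consent.

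**Step 3: size.** The plan gives no figure to reproduce. It states neither the share of Spanish speakers nor a variance for any scale, nor any difference between translators. The following is an illustration only.

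Let *p* be the share of patients who receive translated questionnaires and *d* the proportional increase in their variance of change. Treat the added variation as independent noise and take the simple mean change over all patients. Then:

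- variance factor = (1 − *p*) × 1 + *p* × (1 + *d*) = 1 + *p* × *d*
- effective sample fraction = 1 / (1 + *p* × *d*)
- loss = 1 − 1 / (1 + *p* × *d*)

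Assumed ranges: *p* from 0.20 to 0.40 and *d* from 0.25 to 1.00.

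| *p* | *d* | Variance factor | Effective fraction | Loss |
|---|---|---|---|---|
| 0.20 | 0.25 | 1.05 | 0.952 | 4.8% |
| 0.40 | 0.25 | 1.10 | 0.909 | 9.1% |
| 0.20 | 1.00 | 1.20 | 0.833 | 16.7% |
| 0.40 | 1.00 | 1.40 | 0.714 | 28.6% |

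The documents give two sample sizes, 15 (sections D and F1) and 50 (section G1). The range corresponds to:

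- of 15 patients: 15 × 0.048 = 0.7 to 15 × 0.286 = 4.3
- of 50 patients: 50 × 0.048 = 2.4 to 50 × 0.286 = 14.3

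**Step 4: which quality-of-life form is meant?** Section F2 lists "quality of life (Promise Global General Health Questionnaire" and does not list SF12. Section G2 analyses SF12 and does not mention the other. The exposure is the same for either instrument, but a Spanish form cannot be prepared until the two sections agree.

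**The case against.** The best case for leaving the plan alone is that little depends on these scores. This is a proof-of-concept pilot, and no primary or secondary endpoint in section D rests on questionnaire wording. Within H3 the quality-of-life score stands beside several activity measures. All of that is correct, and it limits the point to a cheap improvement. It does not remove it, because H3 still names quality of life as something to be tested.

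It is also fair to say that section J2 does not describe how the translation will be done. That it will be oral and improvised is an inference from the absence of a Spanish form. What the text does establish is that wording and translator are not fixed.

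A reader might infer more than the documents support:

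- **Cognitive scores.** Section F2 says "The Montreal Cognitive Assessment (MOCA) is a series of questions used to assess cognitive status". But cognition is neither an endpoint in section D nor a dependent variable in section G2, and the attached forms in Section S are not available to show whether this instrument is among them.
- **Perceived benefit.** That questionnaire is answered once, at the end of the study, so there is no change score for a switch of translator to disturb.
- **Bias from an unblinded translator.** No group is blinded, and English speakers' answers are given under the same knowledge of the device. This is a feature of the design, not of translation, and a fixed Spanish text would not remove it.
- **A single firm figure for lost information.** Both inputs are assumed. Fixing the variance increase at a doubling would give only the upper part of the range, 17-29%.

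**Conclusion.** The point stands as a minor one. The plan admits Spanish speakers, declines to translate the questionnaires, repeats them at 4 weeks, and controls neither the Spanish wording nor the translator between visits. For quality of life and fear of falling, a switch therefore enters the within-patient change directly. The perfusion, plantar-pressure and sensor-based results are unaffected.

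The size is not computable from the documents. A loss of about 5-29% of the effective sample for these scales follows only if 20-40% of patients are Spanish-speaking and their variance of change rises by 25-100%. If few Spanish speakers enrol, or the same coordinator happens to use the same words each time, the loss would be close to zero.

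**What to change.** Use one fixed written Spanish version of each repeated questionnaire at both baseline and 4 weeks, taking an existing validated version where there is one. Submit these forms with the Spanish consent document that is already planned.

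If that is not possible, the minimum is:

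- the same coordinator and the same written script for a given patient at both visits;
- the language of administration recorded for every questionnaire;
- questionnaire results reported with and without orally translated cases.

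Before the forms are prepared, reconcile sections F2 and G2 on which quality-of-life instrument is used.

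The cost is some preparation of forms, which grows with the number of repeated scales in section F2, and a small approval delay. It needs no extra patients, visits or procedures. It should be done before enrolment, because baseline scores taken with varying wording cannot be repaired afterwards.
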